Title: Role of Platelet Rich Plasma in supporting the recovery of post-partum Levator Ani Muscle trauma

Running title: Platelet rich plasma in levator ani muscle trauma

NCT number: NCT03021954

Document date: January 15th, 2018

Financial dislaimer: None

Study Analysis Plan (SAP)

• Estimated Sample Size

$$n1 = n2 = 2\left(\frac{(Z\alpha + Z\beta)S}{X1 - X2}\right)^2$$

Information:

n = Number of samples

 α = type I error is set at 5 %, the hypothesis is in the direction of $Z\alpha$ = 1.64

 β = type II error is set at 10 %, the hypothesis is in the direction of Z β = 1,28

X1 - X2 = the minimum difference that is considered significant

- Measurement of the levator hiatal area during valsalva, the researchers set a value of X1-X2 = 5. From the journal about the levator ani hiatus area during Valsalva, it was obtained SD = 6.09. The sample size for each group was 23 subjects.
- Measurement of the strength of the levator ani muscle contraction, the researchers set a value of X1-X2 = 9. From the journal on the strength of the levator ani muscle contraction, it was obtained that SD = 11.63. The sample size for each group was 27 subjects.
- The drop out number of samples is added by 20%. Thus, the total sample is 65 people.

Sampling Method

The sample was taken consecutively. The researcher took subjects who met the inclusion criteria and passed the exclusion criteria until the target number of subjects was met. Randomization using online randomizer. Subjects were divided into two groups, namely the intervention group with PRP injection and the control group.

Daya Analysis

Data were analyzed using Statistical Product and Service Solutions version 20 (SPSS version 20). Univariate analysis was performed for each variable and then presented in terms of frequency and percentage. For the bivariate analysis of the intervention and control groups with certain independent variables used unpaired categorical comparative

analysis of 2 groups using the Mann-Whitney test, paired comparative analysis of 2 groups using the Willcoxon test. If p < 0.25, then multivariate analysis was performed.

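### The declared one-sided 5% level and 90% power do not yield the stated 23 and 27 per group, and the test's sidedness is left open; reported two-sided, power at 27 is about 77 to 81% for strength and 83 to 85.5% for hiatal area

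*SAP*

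**What the plan says.** The SAP's Estimated Sample Size section uses the usual formula for comparing two means with equal groups. It gives the error rates as "type I error is set at 5 %, the hypothesis is in the direction of" Zα = 1.64 and "type II error is set at 10 %, the hypothesis is in the direction of" Zβ = 1.28. The value 1.64 is the one-sided 5% point; the two-sided point is 1.96.

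The formula is applied to two outcomes:

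- Hiatal area: "Measurement of the levator hiatal area during valsalva, the researchers set a value of X1-X2 = 5", and "From the journal about the levator ani hiatus area during Valsalva, it was obtained SD = 6.09". The result given is "The sample size for each group was 23 subjects".
- Contraction strength: "Measurement of the strength of the levator ani muscle contraction, the researchers set a value of X1-X2 = 9", and "From the journal on the strength of the levator ani muscle contraction, it was obtained that SD = 11.63". The result given is 27 per group, the larger of the two. Adding 20% for dropout to 54 gives 64.8, hence the planned total of 65.

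The SAP's Daya Analysis section gives the unpaired comparison as "analysis of 2 groups using the Mann-Whitney test". It states no sidedness, direction or significance level for that test. The only p-value threshold there is 0.25, for entry into multivariate analysis.

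**The concern.** The sample size section declares a directional test, while the analysis section leaves the direction open. Each reading has a cost, and the two costs are alternatives.

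- **Two-sided at 5%, as Mann-Whitney results are commonly reported.** The declared type II error of 10% is too low, and a reader would take a null result as stronger evidence than it is.
- **One-sided toward benefit.** The trial could not conclude that PRP worsened hiatal area or strength. The Protocol's Study Procedure has PRP injected directly into the levator ani, and neither document gives a reason to rule out worsening.

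If sidedness stays unstated, it could also be settled after the p-value is known. Separately, the stated group sizes have to agree with the declared inputs before any power figure can be relied on.

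**Working it through.** **Inputs, all from the SAP's Estimated Sample Size section.** Area: difference 5, SD 6.09, standardised difference 5/6.09 = 0.821. Strength: difference 9, SD 11.63, standardised difference 9/11.63 = 0.774. Stated sizes: 23 and 27 per group.

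**Step 1: reproduce the stated sizes.** n per group = 2 × ((Zα + Zβ) × SD / difference)².

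| Zα + Zβ | Meaning | Area | Strength |
|---|---|---|---|
| 1.64 + 1.28 = 2.92 | one-sided 5%, 90% power (as declared) | 2 × (2.92 × 6.09/5)² = 25.3, so 26 | 2 × (2.92 × 11.63/9)² = 28.5, so 29 |
| 1.96 + 1.28 = 3.24 | two-sided 5%, 90% power | 31.1, so 32 | 35.1, so 36 |
| 1.96 + 0.84 = 2.80 | two-sided 5%, 80% power | 23.3, so 24 | 26.2, so 27 |
| Stated in the SAP | | 23 | 27 |

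The declared inputs do not return the stated sizes. Two-sided 5% with 80% power comes closer, but 23.3 must be rounded down and 26.2 rounded up to reach 23 and 27.

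**Step 2: power at the governing size of 27 per group.** By z-test, power = Φ(standardised difference × √(n/2) − z), with √(27/2) = 3.674.

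- Strength: 0.774 × 3.674 = 2.843. One-sided: Φ(2.843 − 1.645) = 88.5%. Two-sided: Φ(2.843 − 1.960) = 81.1%.
- Area: 0.821 × 3.674 = 3.017. One-sided: Φ(3.017 − 1.645) = 91.5%. Two-sided: Φ(3.017 − 1.960) = 85.5%.

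**Step 3: two-sided 5% power at 27 per group, by method.**

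| Method | Strength | Area |
|---|---|---|
| z-test | 81.1% | 85.5% |
| t-test (noncentral t, 52 df) | 79.7% | 84.1% |
| Mann-Whitney, adjusted by efficiency 3/π | 79.3% | 83.8% |
| Mann-Whitney, 20,000 simulated normal data sets, asymptotic test without continuity correction | 77.2% | 82.9% |

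At the SAP's own 23 per group for area, the figures are 79.5% (z), 77.7% (t) and 75.9% (simulated Mann-Whitney). One-sided by z-test, 23 per group gives 87.3%.

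**Step 4: where the gap from 90% comes from.**

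- Strength: the low n costs 1.5 points (90 to 88.5) and sidedness 7.4 (88.5 to 81.1). Moving from the z-test to the t or rank test costs a further 1.4 to 3.9 (81.1 to 79.7 or 77.2).
- Area: 27 exceeds the 26 that the formula requires, so the start is 91.5%. Sidedness costs 6.0 points (91.5 to 85.5), and the t or rank test 1.4 to 2.6 (85.5 to 84.1 or 82.9).

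**The case against.** The strongest case on the other side is that the SAP openly declares a directional hypothesis at 5%, which is a legitimate design. Nothing in the analysis section says the Mann-Whitney test will be two-sided. Under the declared design the type I error is the stated 5%, and calling this twice the conventional false-claim rate measures it against a convention the SAP did not adopt. This stands: two-sided reporting is a reasonable assumption, not a documented fact. It does not rescue the figures, because strength at 27 per group misses 90% even one-sided.

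Three stronger readings are tempting and should be resisted:

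- **That one-sided alpha alone takes power from 90% to 77 to 85.5%.** Sidedness accounts for 6 to 7 points. The low n for strength and the t or rank test account for the rest.
- **That the trial both loses power and cannot conclude worsening.** The lower power requires a two-sided test, under which worsening can be concluded. The inability to conclude worsening requires a one-sided test.
- **That the test sized is known to differ from the test to be reported, or that the authors really sized for two-sided 5% and 80% power.** The stated 23 and 27 lie closer to that design, but the documents do not show which inputs were used.

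It may also be said that the practical effect is modest. The Protocol's Participant Flow section reports 58 subjects completing. If that is the total, split equally (an assumption), 29 per group gives two-sided z-test power of 83.8% for strength and 87.8% for area, or about 81% and 85% by simulated Mann-Whitney. However, the losses listed there leave 245 − 85 − 39 − 5 = 116, so achieved power cannot be settled from the documents. The point is therefore confined to the planned size.

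**Conclusion.** The concern holds as a mismatch that must be reconciled. The declared one-sided 5% level and 10% type II error require 26 and 29 per group, against 23 and 27 stated, and the analysis section does not fix the sidedness of the test. If the comparison is two-sided at 5%, the type II error at 27 per group is about 19 to 23% for strength and 14.5 to 17% for area, not 10%. If it is one-sided toward benefit, the cost is instead that worsening could not be concluded.

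The power figures assume normal data, equal groups, 27 analysed per group, and the SAP's own differences and SDs. The mismatch between inputs and stated sizes rests on the SAP's formula alone.

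**What to change.** Change the following together in the SAP:

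1. **Estimated Sample Size, error rates.** Declare a two-sided 5% level (Zα = 1.96) and replace the 10% type II error (Zβ = 1.28) with about 20% (Zβ = 0.84). Changing Zα alone would widen the mismatch, because the formula would then return 31.1 and 35.1.
2. **Estimated Sample Size, results.** Give 24 per group for hiatal area (from 23.3) and 27 for strength (from 26.2). The larger figure still governs, so the planned total of 65 is unchanged.
3. **Estimated Sample Size, power.** State the power at 27 per group as about 80% for strength and 84% for hiatal area, slightly less with Mann-Whitney (about 77% and 83% by simulation under normality).
4. **Daya Analysis.** State that all between-arm p-values are two-sided and judged at 5%.

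The Protocol already reports completed follow-up, so the change should be dated and should say whether outcome data had been seen.

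The cost is SAP wording only, with no extra enrolment. The downside is a less favourable stated power than 90%.

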- 1. After perineometry examination, the patient will underwent 3D ultrasonography examination to measure the integrity of the levator ani muscle and levator hiatal area,
- 2. The transducer is wrapped with a condom before placing it on the perineum,
- 3. Imaging is performed when the patient is in a dorsal lithotomy position (the hips are flexed and slightly abducted), after the bladder has been emptied,
- 4. Display a 2D image, position it so that the symphysis pubis, bladder, vagina, anorectal to levator ani are included in the volume which will be displayed in 4D,
- 5. Measure the hiatal area by pressing the point area on the screen and measure the hiatal area by tracing the edge of the hiatal,
- 6. Subjects were asked to do valsalva maneuver 2 times, measuring the left and right LUG (levator urethral gap) distance on 3 central Tomographic Ultrasound Imaging (TUI) images. If the distance is > 25 mm, then there is a levator ani avulsion,
- 7. Wipe the patient's genital area with a tissue and allow the patient to change clothes,
- 8. Ultrasound results will be validated by an expert (which is different from the USG operator).

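### Does the protocol's silence on when the hiatal area is traced break the link with a sample size set for area during Valsalva?

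*SAP*

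**What the plan says.** The SAP, under Estimated Sample Size, sizes two outcomes. For hiatal area it writes "Measurement of the levator hiatal area during valsalva, the researchers set a value of X1-X2 = 5" and then "From the journal about the levator ani hiatus area during Valsalva, it was obtained SD = 6.09", and arrives at 23 per group. For contraction strength it takes a difference of 9 and an SD of 11.63 and arrives at 27 per group. After adding 20% it concludes: "Thus, the total sample is 65 people".

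The protocol describes the scan in Standard Operational Procedure 2:

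- Step 1 gives its purpose: "to measure the integrity of the levator ani muscle and levator hiatal area".
- Step 3 fixes the conditions: "Imaging is performed when the patient is in a dorsal lithotomy position", with the bladder emptied. It names no manoeuvre.
- Step 5 is the only step that obtains the area: "Measure the hiatal area by pressing the point area on the screen and measure the hiatal area by tracing the edge of the hiatal".
- Step 6 is the only place in the protocol where Valsalva appears: "Subjects were asked to do valsalva maneuver 2 times, measuring the left and right LUG (levator urethral gap) distance".

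Study Procedure e (baseline) and h (40 days and 3 months) mention the ultrasound assessment without a state. The SAP's analysis paragraph gives the between-group comparison as "analysis of 2 groups using the Mann-Whitney test" and names neither an outcome nor a state.

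**The concern.** Hiatal area is one of only two outcomes with a sample size behind it, and both its planning inputs are tied to Valsalva. An operator who works through SOP 2 in numbered order traces the area at step 5, before any manoeuvre has been requested, and at step 6 uses the manoeuvre for a different measurement. SOP 1, by contrast, writes out the squeeze that contraction strength requires.

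If the area had been traced in some other state, the ratio 5/6.09 would not describe the reported outcome, and a reader could not rely on the SAP's calculation for it. What is at stake is the match between the planned and the measured outcome.

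**Working it through.** **1. Is there a contradiction or a gap?** Side by side:

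| Place | Area mentioned | State named for area |
|---|---|---|
| SAP, sample size (difference and SD) | yes | Valsalva, twice |
| SOP 2 step 1 | yes | none |
| SOP 2 step 3 | no (imaging conditions) | none |
| SOP 2 step 5 | yes | none |
| SOP 2 step 6 | no (levator-urethral gap) | not applicable |
| Study Procedure e | only as biometry | none |
| Study Procedure h | yes | none |

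One state is named and no other is named anywhere. Step 4 sets up a volume for 4D display, and no step says that the area must be traced before the manoeuvres of step 6. The step order permits a tracing without Valsalva but does not require one. The text supports *does not specify*. It does not support *measures something else*.

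**2. Does the total depend on it?** Inputs are the SAP's printed group sizes and its 20% addition.

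- Strength: 2 × 27 × 1.2 = 64.8, which rounds up to the printed 65.
- Area: 2 × 23 × 1.2 = 55.2.

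The larger figure governs. The printed 23 does not itself follow from the SAP's formula: 2 × ((1.64 + 1.28) × 6.09 / 5)² = 25.3, so 26. For strength, 2 × ((1.64 + 1.28) × 11.63 / 9)² = 28.5, so 29. With those values the totals would be 2 × 26 × 1.2 = 62.4 and 2 × 29 × 1.2 = 69.6, and strength still governs. The 23 is a separate matter and does not bear on the tracing state.

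**3. Can a loss of power for area be computed?** No. The documents give neither a difference nor an SD for area in any other state. As an illustration, hold the difference at 5 and *assume* other SDs. With n = 27 per group and one-sided 5%, power ≈ Φ((5/SD) × √(27/2) − 1.645). For the planned SD: 0.821 × 3.674 − 1.645 = 1.372, so 91.5%.

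| SD | n per group for 90% power | Power at 27 per group |
|---|---|---|
| 4 (assumed) | 11 | 99.8% |
| 5 (assumed) | 18 | 97.9% |
| 6.09 (SAP) | 26 | 91.5% |
| 7 (assumed) | 34 | 83.6% |
| 8 (assumed) | 44 | 74.3% |

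The range runs in both directions, so not even the sign of an effect is established. The difference might also change with the state, which widens the uncertainty further.

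**4. Is the comparison at risk of bias?** Study Procedure h says that the ultrasound operator is unaware of the group, and SOP 2 step 8 has the results validated by a different expert. A choice of state made under that masking cannot depend on treatment. In any one consistent state, the randomised comparison is valid for the area in that state.

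**The case for a change.** The strongest case for a change is that operators work from the SOP, not from the SAP's sample size section. One who traced at step 5 with no manoeuvre would be fully compliant. Nothing in the protocol guarantees the same state at baseline, 40 days and 3 months, and the analysis paragraph does not fill the gap. Writing the state into the SOP would cost a few words.

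Much of this stands as description: the SOP is silent, and a fuller SOP would name the state. It does not carry the point further:

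- The contrast with SOP 1 is weak, since contraction strength cannot be measured at all without asking for a contraction.
- Inconsistency between operators or visits is a possibility that the text leaves open. It is not something that the text shows, and under masking it would add noise to both groups alike.
- The protocol already reports participants who completed follow-up, so rewording the SOP would not alter scans already made. Re-tracing would need stored Valsalva volumes, which the documents never mention.

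**Conclusion.** No change to the plan follows. The protocol leaves out a detail that its companion SAP, with the same title and date, supplies, and nothing in the protocol conflicts with it. A trial team holding both documents would take the area during Valsalva, and a report of the results would ordinarily say in which state the area was measured.

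The total of 65 is unaffected, masking protects the between-group comparison, and the effect on power for area is unknown in both size and direction. The conclusion rests on two assumptions: that the two documents are read together, and that one state was used consistently. Had the documents said that the area was traced in a state other than Valsalva, the 5/6.09 calculation would not apply to the reported outcome and the point would be a real mismatch. They do not say so.

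### The stated 23 and 27 per group do not follow from the SAP's own formula and Z values, which give 26 and 29; power for strength, but not for hiatal area, falls modestly short of 90%

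*SAP*

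**What the plan says.** The SAP's Estimated Sample Size section gives the formula n per group = 2[(Zα + Zβ)S/(X1 − X2)]² and all of its inputs.

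- Type I error: "type I error is set at 5 %, the hypothesis is in the direction of" Zα = 1.64, which is the one-sided 5% value.
- Type II error: "type II error is set at 10 %, the hypothesis is in the direction of" Zβ = 1.28, which is the value for 90% power.
- Hiatal area during Valsalva: "the researchers set a value of X1-X2 = 5" and "it was obtained SD = 6.09". The result is given as "The sample size for each group was 23 subjects".
- Contraction strength: difference 9 and SD 11.63. The result is given as "The sample size for each group was 27 subjects".
- Total: "The drop out number of samples is added by 20%. Thus, the total sample is 65 people".

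The SAP's data analysis section names Mann-Whitney and Wilcoxon tests. It gives no significance level or sidedness for the treatment comparison, so the sample-size section is the only place where these are stated.

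**The concern.** A sample-size statement that prints its formula and every input should be reproducible by hand. This one is not: both per-group figures are lower than the formula gives. The printed error rates and the printed sizes therefore cannot both describe the plan.

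Two things are at stake. First, strength has the larger requirement and so sets the total. If the printed error rates stand, its stated 10% type II error is not met. Second, a reader cannot tell whether the trial was planned for one-sided 5% with 90% power or for something nearer two-sided 5% with 80% power, and no other section settles it.

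**Working it through.** **Inputs** (all from the SAP, Estimated Sample Size): Zα + Zβ = 1.64 + 1.28 = 2.92; area S = 6.09, difference 5; strength S = 11.63, difference 9.

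**Step 1. The printed formula with the printed inputs.**

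- Area: 2 × (2.92 × 6.09 / 5)² = 25.30, so 26 per group. Stated: 23.
- Strength: 2 × (2.92 × 11.63 / 9)² = 28.48, so 29 per group. Stated: 27.

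Rounding does not explain the gap. Rounding down, or to the nearest whole number, gives 25 and 28.

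**Step 2. The total.** 2 × 27 = 54 and 54 × 1.2 = 64.8, so 65. The total is consistent with 27 per group, which is therefore the working size for both outcomes. The same rule applied to 29 per group would give 58 × 1.2 = 69.6, so 70.

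**Step 3. Power at the working size.** Power = Φ[(difference/S) × √(n/2) − z], with z = 1.645 for one-sided 5%:

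| n per group | Strength | Area |
|---|---|---|
| 29 | 90.4% | 93.1% |
| 27 | 88.5% | 91.5% |
| 26 | 87.4% | 90.6% |

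The row for 26 applies only if 20% of the 65 enrolled are lost: 65 × 0.8 = 52, or 26 per group.

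The type II error for strength is thus 11.5% at 27 and 12.6% at 26, instead of 10%. The difference in strength detectable with 90% power is 2.92 × 11.63 × √(2/n), which is 9.24 at 27 and 9.42 at 26, against the SAP's 9.

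**Step 4. Sensitivity to the test, at 27 per group.**

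- t-test: strength 87.7%, area 90.9%.
- Mann-Whitney, taking 0.955 efficiency under normality (an assumption): strength about 87.2%, area about 90.4%.

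Strength is below 90% and area above it by all three methods.

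**Step 5. Could other Z values have been used?** Two-sided 5% with 80% power (1.96 + 0.84 = 2.80) gives 23.26 for area and 26.18 for strength, close to the stated pair. Rounded up, these are 24 and 27, so even this does not give 23. If it was the basis, strength power two-sided is about 81% at 27 per group and 79.7% at 26.

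**The case against.** The arithmetic discrepancy is not in dispute. The case on the other side concerns its weight, its explanation and its remedy.

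- **The effect is small.** Strength loses about 1.5 points of power at 27 per group, and an SD of 11.32 instead of 11.63 would remove the loss (9 × √(27/2) / 2.92 = 11.32). The Participant Flow section of the protocol also reports 58 completers; split evenly, 29 per group would give 90.4%. The smallness stands, and the verdict says so. The 58 does not settle the matter: no split by group is given, and an observed count does not correct a planning figure.
- **The two-sided explanation does not fully fit.** Rounding up, 23 needs a Z sum of 2.723 to 2.784 and 27 needs 2.790 to 2.843. Rounding to nearest, the ranges are 2.754 to 2.814 and 2.817 to 2.870. Neither pair overlaps, so no single Z sum yields both figures under a usual rounding rule. This stands. The two-sided reading is only a possibility, and under it 23 would still need correcting.
- **The 20% is evidently a margin on the required number**, since 54 × 1.2 = 64.8. This is the natural reading of the arithmetic. The 26-per-group figures are therefore conditional on a 20% loss among those enrolled. In that case area is borderline rather than clear: 90.6% by normal approximation, 89.9% by t-test, about 89.4% by Mann-Whitney.
- **Keeping 65 beside a requirement of 29 leaves a new mismatch.** It would, if the 10% type II error were left as the power achieved. It does not if the SAP says plainly that 65 corresponds to 27 per group and about 88% power for strength.

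**Conclusion.** The concern holds. With the SAP's formula and printed Z values the required sizes are 26 (area) and 29 (strength), not 23 and 27, under any rounding. The clearer miss is area, by 3 per group. The one with a consequence is strength, by 2 per group, because strength sets the total.

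At 27 evaluable per group, one-sided power for strength is 88.5% against the stated 90%. Hiatal area is not short, because the trial is sized on 27 and not on 23; at 23 it would have had 87.3%.

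These figures rest on the normal approximation, the SAP's own SDs and differences, and equal groups. The loss of power is modest. What needs correcting is a sample-size statement that contradicts itself and so leaves the design's sidedness and power uncertain.

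**What to change.** Reconcile the printed Z values with the stated sizes.

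- **If 1.64 and 1.28 stand:** correct the required sizes to 26 for area and 29 for strength. Keep the total of 65, and state that it corresponds to 27 evaluable per group, with one-sided power for strength of about 88% (about 87% at 26, if 20% of those enrolled are lost).
- **If other Z values were used:** print them, restate sidedness, alpha and power to match, and correct or explain 23.

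In either case, a clause saying whether the 20% is a margin on the required number or an expected loss among those enrolled would remove a minor ambiguity.

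The cost is SAP wording only, with no extra patients. The stated power for strength becomes less favourable: about 87% to 88% one-sided if the printed values stand, or about 80% two-sided if those were the values used.

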Title: Role of Platelet Rich Plasma in supporting the recovery of post-partum Levator Ani Muscle trauma

Running title: Platelet rich plasma in levator ani muscle trauma

NCT number: **NCT03021954**

Document date: January 15th, 2018

Financial dislaimer: None

STUDY PROTOCOL

Participant Flow

We obtained 245 primigravid women. As many as 85 subjects underwent caesarean section because of clinical indications, 39 subjects were failed to follow the study until the end and 5 subjects were found to have avulsion after 40 days post-partum. Overall, there were 58 subjects who successfully followed the examination until the end of the study.

Study Procedure

- a. All patients who come to Polyclinic in Public Health Center (Puskesmas) will be taken a history and physical examination to determine whether the patient meets the criteria or not,
- b. Patients who met the criteria were provided with information about this study. Patients who are willing will be asked to fill out an informed consent. If the patient refuses to participate in this study, the reasons for refusal must be written,
- c. Randomization was performed and participant were divided into 2 groups (intervention group and control group). Participant will not know the results of randomization. Participant may know the results of randomization at the end of the study,
- d. Initial data collection on study form and approval to participate will be taken. Participants are required to write down their full name, complete address, phone number, and family phone number. This is an attempt to increase the participation rate.
- e. Participant will be examined by ultrasound to assess pelvic floor biometry, perineometry to assess pelvic floor muscle strength,
- f. At delivery day, the participant in intervention group will be taken whole blood for preparation of 32 mL of PRP. After the PRP is ready, it will be injected directly into the levator ani muscle during post-partum perineorrhaphy,
- g. Participant in control group will still have whole blood taken for examination (complete blood count) but no PRP preparation will be carried out. During perrineorrharphy will be injected lidocaine 1%. In this way, it is hoped that the participant will now know that she is in the intervention or control group,

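### The SAP's 20% drop-out allowance does not protect its own 54 women, and the SAP does not say which women the 65 counts or how caesarean exits are covered

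*SAP*

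**What the plan says.** Under Estimated Sample Size, the SAP derives 23 women per group for hiatal area and 27 per group for contraction strength. It carries the larger figure forward: "The drop out number of samples is added by 20%. Thus, the total sample is 65 people". It does not define drop-out and does not mention caesarean section.

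Under Sampling Method, it gives the rule that ends recruitment: "The researcher took subjects who met the inclusion criteria and passed the exclusion criteria until the target number of subjects was met". It does not say at which stage a woman counts toward that target.

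In the protocol's Study Procedure, randomisation is step c. PRP or lidocaine is given at perineorrhaphy on the day of delivery (steps f and g). Participant Flow reports 245 women obtained, 85 caesareans and 58 women completing. It adds: "39 subjects were failed to follow the study until the end and 5 subjects were found to have avulsion after 40 days post-partum".

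**The concern.** A drop-out allowance exists so that the required number remains after the expected losses. Multiplying by 1.2 does not achieve that for a 20% loss; dividing by 0.8 does.

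The second issue is which losses the allowance has to absorb. In the protocol's step order, a woman who has a caesarean is lost after allocation and before any study treatment. The SAP has no term for such exits, yet caesarean is the largest loss to which Participant Flow gives a number. Whether the 20% was meant to cover them depends on what the 65 counts, and the SAP does not say.

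At stake are the SAP's stated 10% type II error and the reader's ability to tell what ended recruitment. If women who left after randomisation were replaced, the end of recruitment depended partly on events after allocation, and the SAP should disclose that.

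**Working it through.** **Inputs.** From SAP, Estimated Sample Size: one-sided 5% (Z = 1.64), type II error 10% (Z = 1.28), strength difference 9 with SD 11.63, 27 per group, 20% added, total 65. From protocol, Participant Flow: 245, 85, 39, 5 and 58. Equal arms follow from the SAP's n1 = n2. The 27 per group is taken as given.

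**1. Reproduce the SAP's total.** 2 × 27 = 54; 54 × 1.20 = 64.8, rounded up to 65. This matches.

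**2. Test the allowance.**
- 65 × 0.80 = 52, or 26 per group, which is 2 below 54.
- 65 − 54 = 11 losses tolerated; 11/65 = 16.9%.
- To keep 54 after a 20% loss: 54/0.80 = 67.5, so 68. Check: 68 × 0.80 = 54.4.

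**3. Cost in power for strength.** Power = Φ[(9/11.63) × √(n/2) − 1.645], with n per group.
- n = 27: 0.7739 × 3.674 − 1.645 = 1.198, so 88.5%.
- n = 26: 0.7739 × 3.606 − 1.645 = 1.145, so 87.4%.

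The slip costs about one percentage point. For hiatal area (difference 5, SD 6.09) the same formula gives 91.5% at 27 and 90.6% at 26, so that endpoint stays above 90%.

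**4. Size of the caesarean exits.** 85/245 = 34.7%. The other losses given a number are 39 + 5 = 44, so caesareans exceed them. The flow does not close, however: 245 − 85 − 39 − 5 = 116, but 58 are reported as completing, which leaves 116 − 58 = 58 women unexplained. If all of those were non-caesarean losses, the other attrition would be 44 + 58 = 102, more than 85. The ranking therefore holds only for the itemised losses.

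**5. What the text permits if the 65 counts women randomised antenatally.**
- After caesareans: 65 × 160/245 = 42.4.
- After a further 20% loss: 42.4 × 0.80 = 34.0, about 17 per group.
- Power for strength: 0.7739 × √(16.98/2) − 1.645 = 0.610, so about 73%.

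**6. What was reported.** The 58 completers exceed 54. With equal arms (assumed, 29 per group), the same formula gives about 90% for strength.

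**The case against.** The SAP says only that 20% is added, and it adds 20%. It never promises that 54 will remain after a 20% loss. This stands as a matter of wording: the SAP did what it says. It does not rescue the allowance, whose only purpose is to preserve the required number.

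The consequence is also small. Two women and about one point of power separate 65 from what a 20% loss would require. The larger part of the shortfall, from the stated 90% to 88.5%, is present at 27 per group with no losses at all. It comes from the base sample size, which is a separate point, and printing 68 would not remove it. All of this stands.

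A reader might infer that a target of 65 and a recruitment of 245 contradict each other. The documents do not show that. They do not list the entry criteria, and the target could refer to a later stage, such as women delivered vaginally or women completing. What can be shown is that the counting unit is undefined.

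A reader might also take 39/160 (24.4%) as the loss rate after vaginal delivery and project evaluable numbers from it. With 58 women unexplained, Participant Flow does not support that rate.

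Finally, a reader might conclude that the trial ended underpowered because of caesareans. The 58 reported completers exceed the SAP's 54, so the documents do not support that either.

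**Conclusion.** The point holds and is minor. The 65 protects the SAP's 54 against 11 losses (16.9%), not against 20%. At a 20% loss, power for strength is 87.4% instead of 88.5%.

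The more consequential gap is that the SAP does not say whom the 65 counts or how exits between randomisation and treatment are covered. On one permitted reading, women randomised antenatally, about 34 women and about 73% power would remain.

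That scenario assumes that the 34.7% caesarean share of the 245 applies to randomised women, that the 20% loss comes on top of it, and that the arms stay equal. It describes what the wording allows, not the trial's result.

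**What to change.** - **Allowance.** Restate it as what 65 delivers: 11 losses (16.9%), and about 87% power for strength after a 20% loss. If 20% is kept as the planning figure, print 68 instead.
- **Counting unit.** State which event the 65 counts, consistently with randomisation at step c of the Study Procedure. The text should not say that randomisation followed vaginal delivery, because step c places it earlier.
- **Exits and replacement.** State whether women who left after randomisation, including by caesarean, were replaced.
- **Reconciliation.** Reconcile the 65 with the 245 obtained and the 58 completing, and account for the 58 unexplained women. Until that is done, do not print a loss rate of 24.4% or any evaluable number or power derived from it.

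The cost is wording and a slightly less favourable stated figure. No extra patients are needed if 65 is kept and the figure restated. Participant Flow already reports recruitment and completion in the past tense, so the change is a clear account of what was done, not a new recruitment rule.
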